#### **Background:**

The COVID-19 pandemic has led to a very rapid development of novel vaccines for the SARS-COV-2 virus. The first two vaccines to show over 90% efficacy in phase III trials include novel mRNA vaccines produced by Pfizer /BioNtech, and Moderna. Although these vaccines have, or likely will soon been approved for use in Canada (Pfizer approved on December 9, 2020, Moderna under review), the details of the immune response to the vaccine remain unclear. In particular, questions remain regarding the duration of protection, the correlates and mechanisms of protective immunity, and the durability of immunity among those with immune-compromising comorbidities.

Vaccine efficacy and population-level immunity to infection requires both effective antibody responses (mediated by B-cells) and cell-mediated immunity (CMI; mediated through T-cells). The Pfizer vaccine, BNT162b1, a lipid nanoparticle-encapsulated mRNA vaccine targeting the receptor binding domain (RBD) of the SARS-CoV-2 spike protein, has been shown to produce robust neutralizing antibody responses in a wide range of individuals of diverse age and ethnicity , consistent with responses observed in recovered convalescent COVID-19 patients. Less is known about the T cell-mediated CMI response. A small study (60 participants) has shown T cell responsiveness to the vaccine in those under 55 . These individuals were all healthy and had little ethnic diversity. Furthermore, the assessment of the T cell response was very basic and no information on the T cell subtypes, phenotypes or function (other than interferon (IFN)-gamma production) was assessed.

Although the presence of antibodies is commonly used as an indicator of protective immunity following vaccination or infection, it may not be the only, nor the key, correlate of immune protection. Indeed, CMI responses are necessary for mounting proper antibody responses in addition to other immune functions. CMI responses to viral infection generally involve different classes of T cells including CD8+ cytotoxic T lymphocytes (CTLs), which kill infected cells, and CD4+ T-helper (Th) cells, which vary by subset in their ability to enhance CTL and antibody responses (Th1 and TFH), modulate immunity at mucosal surfaces (Th17) and regulate these responses and limit tissue damage (Tregs) . Each of these T cell subsets is critical for an effective and long-lasting immune response; however, their function varies between individuals due to intrinsic factors, including genetic background, infection history, lifestyle and comorbidities. Variability in CMI responses has been observed in COVID-19 patients and has been associated with disease severity . This variability can similarly be expected to impact the ultimate efficacy of a SARS-CoV2 vaccine.

Much remains to be learned about the immune response to the new COVID-19 vaccines. This study will aim to assess the diversity and complexity of the CMI response to the COVID-19 vaccine. Importantly, we will monitor vaccine induced responses in both healthy groups, as well as those with co-morbid conditions including diabetes and kidney disease.

# **Objectives:**

This study aims to address the following three objectives:

1. Longitudinal evaluation of the development of CMI responses in response to SARS-CoV-2 Vaccine: T cells isolated from the blood of COVID-19 vaccine recipients will be evaluated for their functionality in response to vaccine antigens. The temporal and functional properties of CMI responses will be correlated with the humoral or antibody responsiveness. CMI responses will be measured in vaccine recipients prior to vaccination to determine whether the presence or functionality of pre-existing responses to common cold coronaviruses (CCCs) or previous SARS-CoV-2 infections affect the development of CMI responses to the COVID-19 vaccine.

2. Identification of cellular and soluble factors that influence vaccine responsiveness:

While we know poor clinical outcomes in COVID-19 patients are strongly associated with markers of systemic inflammation, the influence these systemic markers will have on COVID-19 vaccine responsiveness is not clear. Using systems biology approaches, we will perform comprehensive profiling of cellular immune subsets, inflammatory signatures to identify determinants influencing the development of CMI responses to vaccine.

3. Examine variability of immune and viral genes and their relationship to vaccine induced immune responses: Human leukocyte antigen (HLA), T cell receptor (TCR) and

B cell receptor (BCR) proteins are highly genetically diverse and critical to development of protective immunity. We will perform HLA sequencing on whole blood-derived DNA samples and TCR and BCR sequencing on sorted, SARS-CoV2 vaccine antigen-specific T cells and B cells, respectively, to assess how different sequence combinations impact the CMI responses to vaccine.

## **Methodology**

## a) Study Populations

Study populations will include individuals being administered one of the approved SARS-CoV-2/ COVID-19 vaccines. Several clinics within the Health Sciences Centre and microbiology laboratory staff in Winnipeg will be accessed to include both healthy participants as well as those with underlying health conditions known to increase risk for COVID-19 disease severity.

## Front line health care workers (hospital or laboratory) n=100

In partnership with [name] who is currently running an occupational health screening program exposed health for COVID-19 care workers (HCW) at the Winnipeg Health Sciences Centre, we will enroll participants scheduled to be receiving the COVID-19 vaccine. In addition we will work with [name] at the Cadham Provincial Laboratory to facilitate enrollment of laboratory workers scheduled to receive the vaccine.

We will also enroll study participants from the National Microbiology Lab, including staff members at the Canadian Science Centre for Human and Animal Health and the JC Wilt Infectious Diseases Laboratory in Winnipeg who are scheduled to receive the COVID-19 vaccine

# Dialysis Patients n=100

In collaboration with [name] who heads the renal program at the Winnipeg Health Sciences Centre, we will enroll dialysis patients from the renal program scheduled to be receiving the COVID-19 vaccine.

**b) Recruitment**: The study protocol, recruitment, consent to participate forms, and use of data are intended to comply with ethical principles set out in the 2nd edition of the Tri-Council Policy Statement (TCPS 2) for the ethical conduct for research involving humans.

Participants at least 18 years of age or older attending the various clinics will be asked by a clinic nurse/physician if they are willing to participate in a study on vaccine induced immunity. If they agree to participate, a study nurse will approach the participant using the verbal script for recruitment. Participation in the study is entirely voluntary and participants can withdraw from the study at any time. Participants receiving any Health Canada approved COVID-19 vaccine are eligible to participate.

c) Informed Consent: The study nurse will describe the nature of the study, provide a brief description of the use of the samples, and discuss issues of confidentiality, and any risks or benefits associated with the provision of the samples. All participants must provide informed consent prior to the collection of samples.

### d) Questionnaire/Study Instruments

Participant Enrollment Questionnaire: Together with the research nurse, participants will be asked to fill out a basic questionnaire at the time of enrollment. This form will collect basic demographic and clinical information critical for analysis of potential drivers or confounders of observed CMI responsiveness to vaccine:

- Date of enrollment and first sample collection
- Demographics: Age, sex, height, weight, ethnicity
- Pre-existing co-morbidities
- Current Medications
- Whether participant received annual flu shot

Participant Follow Up Questionnaire: On subsequent study visits, returning participants will be asked to answer some questions on whether they experienced any side effects following vaccination or if they have experienced any COVID-19 like symptoms or have had COVID-19 test since their last study visit.

Data Extraction Form: Participants who consent will have relevant clinical data extracted from their medical records. A research coordinator will extract information from patient charts pertaining to pre-existing comorbid conditions and the clinical measurements used to monitor the severity and treatment of that condition. These will then be used to determine if they are associated with CMI responses to vaccine in multivariate analysis.

#### e) Sample Collection

Participants will be approached prior to receiving their first dose of COVID-19 vaccine, and will consent to sampling pre and post vaccination. The specimens to be collected include:

At each sampling timepoint, study personnel will collect:

• 4 tubes of EDTA blood: taken from a vein in the arm. This will be used to isolate immune cells for evaluation of CMI responses (Objective 1), cellular biomarkers

(Objective 2) and analysis of immune genes (Objective 3), and blood plasma for analysis of soluble biomarkers (Objective 2). Collected at all time points

- 1 NP swab in one nostril: a swab is inserted along the nasal septum to the nasopharynx and rotated for approximately 5 seconds to collect secretions then deposited into a tube containing transport medium. This will be used to evaluate cellular and soluble biomarkers (Objective 2). Note that an NP swab will ONLY be collected at time points 1, 3 and 4.
- 1 buccal swab: a swab is inserted into the mouth and brushed against the inside of the cheek then deposited into a tube containing transport medium. This will be used to evaluate soluble biomarkers (Objective 2). Collected at all time point
- 1 saliva sample: participant spits saliva into a collection tube. This will be used to evaluate soluble biomarkers (Objective 2).Collected at all time points

## f) Sampling Schedule

- 1. **Day 1:** (Baseline sample) At the time of enrollment / prior to receiving the first dose of the COVID-19 vaccine
- 2. Day 3-4: After the initial first vaccine dose
- 3. Day 10-14 post first vaccine dose

4.

- Day 21: Prior to receiving the second vaccine dose 4. Day10-14 post second vaccine dose : Approximately 2 weeks post second vaccine dose 2 month post second vaccine dose
  - 6. 4 months post second vaccine dose
  - 7. 6 months post second dose: Long term sampling timepoint at 6 months
  - 8. 1 year post second vaccine dose; : Long term sampling timepoint at 1 year

# g) Logistics and Approvals

Samples will be transported by study personnel to the JC Wilt Infectious Diseases Research Centre where researchers will process and store specimens for further analysis.

Necessary study approvals and agreements will be in place prior to commencing participant enrollment. These include impact assessments for accessing patients and health records at the Health Sciences Centre, and approvals from the Assembly of Manitoba Chiefs, Health Information Research Governance Committee (HIRGC), as we are collecting ethnicity data.

# h) Testing and Analyses

The different biological readouts for our study will vary by type of test and analysis, as outlined below.

*Objective 1* – CMI responses: Cells isolated from the blood samples collected will be exposed to the COVID-19 vaccine antigens or other common viruses as a comparison (e.g. CCCs, influenza). The ability of the cells to produce immune mediators in response to viral antigens will be quantified by flow cytometry. Global responsiveness to vaccine antigen stimulation will also be assessed via transcriptomics (mRNA profiling). These responses will be compared to similar responses observed in natural infected individuals with disparate disease outcome (Separate PHAC study) as an indicator of vaccine response success. CMI responses will be correlated with the humoral or antibody responsiveness tested by a number of serological assays / platforms including: two different POC rapid cassette / lateral flow antibody assays, the Roche NP and quantitative anti-RBD platforms and also by plaque reduction neutralization and /or surrogate neutralisation assays.

*Objective 2* – Inflammatory Signatures: Plasma samples, swabs and saliva will be analyzed for levels of inflammatory cytokines, chemokines, biomarkers of vascular dysfunction and profiles of regulatory RNA in serum exosomes. Inflammatory biomarkers will be evaluated as determinants of CMI responsiveness to vaccination.

*Objective 3* - HLA sequencing will be performed on whole blood-derived DNA samples from infected individuals. TCR and BCR sequencing will be performed on sorted, SARS-CoV-2 vaccine-specific T- and B-cells using the 10X Genomics platform to assess how different combinations impact infection outcome. Genetic sequencing data cannot and will not be used to identify individuals.

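### The testing section and Objective 3 disagree on who is HLA-typed and on which outcome the TCR/BCR sequences are related to

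*Combined protocol and SAP*

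**What the plan says.** Objective 3 is described twice in the combined protocol and SAP.

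- **Objectives, Objective 3:** "We will perform HLA sequencing on whole blood-derived DNA samples and TCR and BCR sequencing on sorted" vaccine antigen-specific T and B cells, "to assess how different sequence combinations impact the CMI responses to vaccine". Infection status is not mentioned.
- **Section h) Testing and Analyses, Objective 3:** "HLA sequencing will be performed on whole blood-derived DNA samples from infected individuals". The next sentence plans TCR and BCR sequencing on sorted vaccine-specific cells "to assess how different combinations impact infection outcome".

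Four other places bear on the point.

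- **Section a) Study Populations:** "Study populations will include individuals being administered one of the approved SARS-CoV-2/ COVID-19 vaccines". The planned numbers are 100 health care or laboratory workers and 100 dialysis patients.
- **Section e) Sample Collection:** the EDTA blood is assigned to "analysis of immune genes (Objective 3), and blood plasma for analysis of soluble biomarkers (Objective 2). Collected at all time points".
- **Section d) Questionnaire/Study Instruments:** at follow-up, returning participants are asked about side effects and "if they have experienced any COVID-19 like symptoms or have had COVID-19 test since their last study visit".
- **Analysis Plan:** the data from all objectives are to feed models of a successful CMI response. Infection outcome is not named.

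**The concern.** Section h) is the operational section: it tells the laboratory whose DNA to type and the analyst what to relate the sequences to. On both counts it differs from the objective it is meant to carry out.

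The first mismatch is the population, and it affects only the HLA sentence. A subset chosen on infection is not a neutral sample of vaccine recipients. Objective 1 itself asks whether "previous SARS-CoV-2 infections affect the development of CMI responses to the COVID-19 vaccine", so the protocol already treats infection as a possible influence on the response under study. HLA associations found among infected people need not hold for vaccine recipients in general.

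The second mismatch is the outcome, and it affects only the TCR/BCR sentence. The cells in that sentence are vaccine-specific, so its population is sound, but it names an endpoint that no section defines.

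With two populations and two outcomes on paper, the choice between them could be made after the data have been seen.

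**Working it through.** **Textual comparison.** The protocol states no figure on this point, so the check sets the sections side by side.

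| Item | Objectives, Objective 3 | Section h), Objective 3 | Rest of the protocol |
|---|---|---|---|
| Source of HLA samples | Whole-blood DNA, no infection restriction | Infected individuals | Entry by vaccination (section a); blood for immune genes at all time points (section e) |
| TCR/BCR cells | Vaccine antigen-specific | Vaccine-specific | No conflict |
| Outcome for TCR/BCR sequences | CMI response to vaccine | Infection outcome | CMI response is the modelling target (Analysis Plan) |
| Definition of infection outcome | Not needed | None | Follow-up questions on symptoms and tests only (section d) |

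Two readings might reconcile the sections; neither does.

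1. *Infected means vaccinees with an earlier SARS-CoV-2 infection.* HLA typing would still be confined to a subgroup that Objective 3 does not specify, and the outcome would still differ.
2. *Infected means people in the separate PHAC study.* Section h) cites that study only under Objective 1, as a comparator. Under Objective 3 it is not mentioned, and the outcome for the vaccine-specific cells would still differ.

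**Illustration of what a restricted sample could cost.** The only protocol input is N = 100 + 100 = 200. Everything else is assumed: 5-20% infected (200 × 0.05 = 10 to 200 × 0.20 = 40 typed), one allele with a given carrier frequency, a standardised carrier difference d in a CMI readout, and a two-sided t-test.

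With n₁ carriers and n₂ non-carriers, the noncentrality is δ = d·√(n₁n₂/N) on N − 2 degrees of freedom. Power is P(|T| > t at 1 − α/2), with T noncentral t. For d = 0.5, 20% carriers and α = 0.05:

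| N typed | n₁ / n₂ | δ | Critical t | Power |
|---|---|---|---|---|
| 200 | 40 / 160 | 0.5·√32 = 2.828 | 1.972 | 80.4% |
| 40 | 8 / 32 | 0.5·√6.4 = 1.265 | 2.024 | 23.4% |
| 20 | 4 / 16 | 0.5·√3.2 = 0.894 | 2.101 | 13.5% |
| 10 | 2 / 8 | 0.5·√1.6 = 0.632 | 2.306 | 8.7% |

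Sensitivity of power to the assumptions:

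| Setting | N = 200 | N = 40 | N = 20 | N = 10 |
|---|---|---|---|---|
| 10% carriers, d = 0.5, α = 0.05 | 56.0% | 15.2% | 9.7% | 7.0% |
| 30% carriers, d = 0.5, α = 0.05 | 89.7% | 29.2% | 16.3% | 9.8% |
| 20% carriers, d = 0.3, α = 0.05 | 39.3% | 11.5% | 8.0% | 6.3% |
| 20% carriers, d = 0.8, α = 0.05 | 99.5% | 50.5% | 27.3% | 14.6% |
| 20% carriers, d = 0.5, Bonferroni for 20 alleles (α = 0.0025) | 41.0% | 3.3% | 1.3% | 0.6% |
| 20% carriers, d = 0.8, Bonferroni for 20 alleles (α = 0.0025) | 92.6% | 13.2% | 3.9% | 1.2% |

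The absolute levels move a great deal with the assumptions. The loss from 200 to 40 or fewer is large in every row.

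**The case against.** The strongest reply is that this is a drafting ambiguity unlikely to be acted on. The Objectives section is silent on infection rather than opposed to it, and section h) does not say that only infected people will be typed. Sections a) and e) and the Analysis Plan all point to vaccine recipients and CMI response, and the TCR/BCR cells are vaccine-specific. The heading of Objective 3 also mentions viral genes, so infection may not have been wholly outside its scope. If the separate PHAC study was meant, no enrolled subset is selected. Finally, every input to the power figures except 200 is assumed, they pool two quite different cohorts without adjustment, and the protocol makes no power claim for HLA.

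Part of this stands. The harm depends on section h) being followed literally, the documents do not show whether the wording is a slip, and the power figures show scale but prove nothing about intent.

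The rest does not remove the problem. That other sections agree with the Objectives section shows that section h) is out of line; it does not repair it. The viral-genes heading still ends by naming vaccine-induced immune responses, and no viral sequencing is described under it. Two separate phrases point to infection, and the outcome wording is a direct mismatch on any reading.

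**Conclusion.** The concern holds. Section h) departs from Objective 3 in two respects: the source of the HLA samples, and the outcome for the TCR/BCR sequences. Both rest on the current text alone, and confidence in them is high.

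The practical size is conditional. Read literally, section h) would leave HLA typing on an unknown fraction of the 200 participants, selected on a factor that may itself alter the response, and would give the receptor analysis an endpoint without a definition. The illustrative fall in power from 80% to between 9% and 23% rests on assumed infection, carrier and effect figures and should not be quoted as a property of this study.

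This should be fixed: Objective 3 cannot be carried out consistently as written. The mismatch is confined to that objective.

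**What to change.** The sponsor should reconcile the two sections and state which is meant.

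- **If the Objectives section is the intent:** in section h), Objective 3, change the HLA source from infected individuals to all consenting vaccine recipients in both cohorts. Change the TCR/BCR outcome from infection outcome to the CMI response to vaccine, measured by the Objective 1 readouts.
- **If an analysis of infected people is also intended**, whether infected enrollees or the separate PHAC study: list it as a separate analysis. Say who counts as infected and how that is ascertained, and define the outcome.

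The cost is two changes of wording, plus one statement if the second case applies. No new blood is needed, since section e) already collects it for this objective at every time point. Any extra HLA typing is work that the Objectives section already promises. The consent form is not in the text available to me, so the sponsor should confirm that it covers genetic typing of all participants.

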## Analysis Plan:

The data collected from these various objectives will be assembled to develop models for successful CMI responses to COVID-19. Demographic and clinical variables collected will be used to stratify study groups and will be incorporated into multivariate analysis models in consultation with a biostatistician to identify confounders or true associations. In addition, should the study numbers allow, we will stratify data based on vaccine administered to identify variations of immune responses to different vaccine formulations (ie: Pfiezer vs Moderna).

As we do anticipate over-representation of indigenous ethnicity among participants enrolled in the dialysis clinic, even though stratification based on ethnicity is not a primary objective of this study, should we observe any differences in vaccine responses due to ethnicity, this data may serve as preliminary data for future research to be done in consultation with indigenous health research representation.

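### Could a dialysis effect be reported as an ethnicity or vaccine-product difference because the Analysis Plan does not name cohort as a model term?

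*Combined protocol and SAP*

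**What the plan says.** The Methodology section defines two groups, "Front line health care workers (hospital or laboratory) n=100" and "Dialysis Patients n=100". For the second, "we will enroll dialysis patients from the renal program scheduled to be receiving the COVID-19 vaccine".

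The Analysis Plan bears on this point in three places:

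- **General modelling.** Demographic and clinical variables are to be used for stratifying the study groups, and they "will be incorporated into multivariate analysis models in consultation with a biostatistician to identify confounders or true associations".
- **Vaccine product.** If numbers permit, "we will stratify data based on vaccine administered to identify variations of immune responses to different vaccine formulations".
- **Ethnicity.** The authors write that "we do anticipate over-representation of indigenous ethnicity among participants enrolled in the dialysis clinic". They add, "even though stratification based on ethnicity is not a primary objective of this study", that "should we observe any differences in vaccine responses due to ethnicity, this data may serve as preliminary data for future research", with that research to be done in consultation with Indigenous health research representation.

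The Questionnaire/Study Instruments section collects age, sex, ethnicity, comorbidities and medications at enrolment, and describes them as potential drivers or confounders of response. Chart extraction adds measures of the severity and treatment of comorbid conditions, also for multivariable analysis. The Recruitment section makes recipients of any Health Canada approved vaccine eligible, in either group.

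**The concern.** Ethnicity is expected to be associated with cohort, and cohort may well affect response: the Background asks about immunity in people with immune-compromising comorbidities, and the section on expected outcomes describes the patient groups in those terms. These are the ingredients of confounding, and the plan itself announces the imbalance. The sentence quoted from the Analysis Plan then uses causal wording for any ethnic difference and does not condition on cohort. A reader can picture a pooled comparison of Indigenous with other participants that partly compares dialysis patients with workers.

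Product raises a similar worry. It is not randomised, and it could follow the place where the vaccine is given.

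At stake is an ethnic or product difference carried forward as preliminary data when only a dialysis effect exists. The study treats ethnicity as sensitive: Logistics and Approvals ties a governance approval to its collection.

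**Working it through.** **Inputs from the documents.** Two cohorts of 100. An expected but unquantified excess of Indigenous participants in dialysis. No alpha, power, effect size or sample-size derivation is stated, so there is no figure of the plan's own to reproduce.

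**Assumptions.** The Indigenous share in each cohort, a dialysis deficit D in within-cohort SD units (0.5 or 0.8), no true ethnicity effect, and a two-sided 5% test.

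**Step 1: how much of D shows up as a crude ethnicity difference.**

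Leak = P(dialysis | Indigenous) − P(dialysis | other); spurious difference = D × leak.

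With 50% Indigenous in dialysis and 10% among workers there are 60 Indigenous and 140 other participants. The leak is 50/60 − 50/140 = 0.833 − 0.357 = 0.476. At D = 0.8 the spurious difference is 0.8 × 0.476 = 0.38 SD.

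**Step 2: crude false-positive rate.**

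Each group's variance is 1 + D²p(1 − p), where p is its dialysis fraction. In the same case these are 1 + 0.64 × 0.833 × 0.167 = 1.089 and 1 + 0.64 × 0.357 × 0.643 = 1.147. The SE is √(1.089/60 + 1.147/140) = 0.162, and 0.381/0.162 = 2.35. By the normal approximation the test rejects in about 65% of studies. A simulation of 5,000 data sets gave 64.6% crude and 5.2% with cohort in the model.

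**Step 3: price of adjusting for cohort.**

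Variance inflation = 1/(1 − φ²), where φ is the ethnicity-cohort correlation; the SE rises by its square root. At 50%/10%, φ = 0.436, inflation is 1.24 and the SE rises by 11%.

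| Indigenous share, dialysis/workers | Leak | Spurious difference, false-positive rate, D = 0.5 | Same, D = 0.8 | SE increase with cohort |
|---|---|---|---|---|
| 10%/10% | 0 | 0, 5% | 0, 5% | 0% |
| 20%/10% | 0.196 | 0.10 SD, 8% | 0.16 SD, 12% | 1% |
| 30%/10% | 0.312 | 0.16 SD, 14% | 0.25 SD, 27% | 3% |
| 30%/5% | 0.433 | 0.22 SD, 21% | 0.35 SD, 43% | 6% |
| 50%/10% | 0.476 | 0.24 SD, 33% | 0.38 SD, 65% | 11% |
| 50%/5% | 0.564 | 0.28 SD, 42% | 0.45 SD, 78% | 16% |

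For 50%/5% and D = 0.5, a simulation of 4,000 data sets gave a crude bias of 0.28 SD against Indigenous participants and a 41% false-positive rate. With cohort in the model the bias was 0.00 and the rate 5%. That return to 5% follows from how the data were built, since cohort was the only confounder.

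**Step 4: is the effect lost?** Only if the split is total (100%/0%) does adjustment fail. Over-representation means partial confounding, and the ethnicity effect remains estimable with cohort in the model.

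**Step 5: does the plan lead to the crude analysis?** The ethnicity sentence sets no pooled contrast, test or rule of attribution. The general modelling sentence in the same section provides for stratifying the study groups and for multivariable models. If the study groups are the two cohorts defined in the Methodology, which is the natural reading, stratifying them by ethnicity is already a within-cohort analysis. Dialysis status is a clinical variable that defines half the sample. It would be hard for a biostatistician looking for confounders to leave it out, particularly as the ethnicity sentence opens by pointing to the imbalance.

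**Step 6: product.** The same arithmetic applies, but the leak is zero if the product mix is equal in the two cohorts. The documents give no mix, allow any approved product in both cohorts, and make the comparison conditional on numbers. A problem here is possible but not shown.

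**The case for a change.** The strongest case for a change is that a general promise to look for confounders is weaker than a commitment to adjust for one already known. The plan names no model, no outcome and no mandatory term. The imbalance is foreseen, the ethnicity finding is meant to seed further research, the matter is sensitive, and naming cohort would take one sentence and need no new data. At strong imbalance the crude error rate is far above 5%.

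Part of this stands. Cohort is not named for the ethnicity contrast, and the causal wording is looser than an observational comparison can support. But both are matters of detail within an approach that is already sound. Nothing in the plan selects the confounded analysis, and the large error rates belong to an analysis it does not prescribe. Naming cohort would not settle attribution either: diabetes and other comorbidities could still confound ethnicity within dialysis, and for those the plan's broader provision for clinical covariates is the relevant safeguard. The exploratory, non-primary status of the reading, and the consultation planned for any follow-on research, further limit the harm.

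**Conclusion.** No change to the plan is needed. Partial confounding of ethnicity with dialysis status is real by the plan's own expectation. An unadjusted pooled contrast would mislead to a degree that depends on unstated quantities: false-positive rates of about 8% at 20%/10% and a 0.5 SD deficit, and about 65% at 50%/10% and 0.8 SD. All shares and deficits are assumptions. The plan's stratification and multivariable modelling, followed in the ordinary way, bring cohort into the analysis and remove the bias due to cohort for roughly 1% to 16% in standard error across the imbalanced cases shown. Residual confounding by other comorbidities would remain possible under any wording. The product concern has no support in the documents unless the product mix turns out to differ between cohorts. This is a gap in detail that analysts would fill sensibly, in a secondary and preliminary reading.
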